**Table 2 Full Mayo Scale Subscores**

Components	Subscore	Severity	Score
		Normal number of stools for patient	0
	Stool Frequency a (daily)	1 to 2 stools more than normal	1
		3 to 4 stools more than normal	2
		≥5 stools more than normal	3
		No blood seen	0
CLINICAL RESPONSE  (Patient's Symptoms)	Rectal Bleeding b (daily)	Streaks of blood with stool	1
		Obvious blood with stool	2
		Blood alone passes	3
			Normal
	Physician's Global Assessment	Mild disease	1
		Moderate disease	2
		Severe disease	3
ENDOSCOPIC RESPONSE  (Objective Evidence of Inflammation)	Endoscopic Appearance c	Normal	0
		Mild disease	1
		Moderate disease	2
		Severe disease	3

a Each patient serves as his or her own control to establish the degree of abnormality of the stool frequency.

b The daily bleeding score represents the most severe bleeding of the day.

c Endoscopic appearance: Normal, Mild (erythema, decreased vascular pattern, granularity), Moderate (marked erythema, loss of vascular pattern, any friability, erosions), Severe (spontaneous bleeding, ulceration).

Note: endoscopic appearance is not part of the partial Mayo score. In addition, the criteria of endoscopic appearance assessment in this study are DIFFERENT from the original criteria in (13). The Endoscopy subscore is modified so that a value of 1 does not include friability.

Image handling and instructions for endoscopy will be provided to the central reading center from all investigational sites directly or from the sponsor (or CRO).

The patient reported Mayo subscores comprise stool frequency and rectal bleeding. They are collected for up to 5, but at least 3 days prior to each trial visit throughout the trial by the patient at home, and they are collected in both screening and treatment periods. The Mayo Score is not copyrighted. The patient reported Mayo subscores will be collected in electronic format (FDA 21 CFR part 11 compliant) via the use of a Paper Diary.

### 7.1.2 Physical Examinations

A complete physical examination including general appearance, head, eyes, ears, nose, and throat (HEENT), neck, cardiovascular, thorax/lungs, breasts, abdomen, genitourinary, musculoskeletal, lymph nodes, skin, neurological and mental status examination, height (at Screening only), and

body weight will be performed by the Investigator or a delegated Sub-Investigator (a medically licensed qualified trial team member) at Visits 1 (Screening) and 9 (Follow-up). Body weight only will be measured at Visits 1.1, 4, 6 and 8.

The same individual should preferably perform all physical examinations for a patient during the course of the trial. The Investigator will evaluate the clinical significance. Pre-existing conditions diagnosed through assessments and examinations at the screening visit or during the screening period are not adverse events, but are recorded as medical history. If any clinically significant abnormal findings are discovered after informed consent or any pre-existing conditions worsen during the trial, these must be recorded as adverse events.

### **7.1.3 Vital Signs**

Vital signs will be measured at Visits 1, 1.1, 3, 4, 5, 6, 7, 8 and 9 and will include blood pressure (measured after the patient has been in a seated position for  $\geq 3$  minutes of rest), pulse, respiration rate, and body temperature.

The Investigator should evaluate the clinical significance of the results. Clinically significant abnormal findings will be reported as adverse events.

### **7.1.4 Clinical Safety Laboratory Parameters**

Laboratory parameters: urinalysis (dipstick), urine pregnancy test, urine drug panel, haematology, clinical chemistry, coagulation, serum pregnancy test, TB, HIV, HBV, HCV, EBV, and CMV infection test, Clostridium difficile assay, erythrocyte sedimentation rate [ESR], C-reactive protein (CRP), neutrophil and platelet count, and biopsy samples ([Appendix 2](#)) will be measured at local sites according to the schedule in [Table 1](#).

Anti-TJ301 antibodies, Pharmacokinetics TJ 301, IL-6, IL-6/sIL-6R complex, and faecal calprotectin tests will be analysed in central lab; sample collection methods and handling procedures will be described in a separate laboratory manual.

The Investigator will review the laboratory results and evaluate and document whether the results are normal or abnormal and whether abnormal results are non-clinically significant or clinically significant. Pre-existing clinically significant conditions diagnosed as a result of the screening procedures must be recorded as medical history. If any clinically significant abnormal findings are discovered after informed consent or any pre-existing conditions worsen during the trial, these must be recorded as adverse events. The laboratory report will be signed and dated by the Investigator.

For female subjects, a serum  $\beta$ -HCG and a serum pregnancy test will be conducted at the Screening Visit (Visit 1) and urine pregnancy tests will be conducted at visit 8 and Follow-up visit.

### **7.1.5 Electrocardiogram**

In this trial, a routine 12-lead ECG will be performed at Visits 1, 1.1, 3, 4, 5, 6, 7, 8, and 9. The ECG measurements will include heart rate and PR, QRS, and QT intervals. The Investigator will

evaluate the clinical significance of the ECGs. Clinically significant abnormal findings will be reported as adverse events.

## **7.2 Trial-specific Blood and Faeces Sampling**

Blood sampling for exploratory biomarkers (ESR, IL-6, IL-6/sIL-6R complex, and neutrophil and platelet count), faeces sampling for calprotectin assessment, and blood samples for TJ301 and anti-TJ301 antibodies will be performed according to the schedule in [Table 1](#).

## **7.3 Other Assessments**

Not applicable.

### **7.3.1 Demography**

Demographic data will be collected at the Screening Visit, including gender, date of birth, race, and ethnic origin (to the extent allowed by local regulations).

### **7.3.2 Medical and Surgical History**

Information on clinically significant previous and concomitant illnesses, other than UC, or any clinically significant signs or symptoms that are present before informed consent, or pre-existing conditions identified through findings from assessments and examinations done during the Screening Visit will be recorded as medical and surgical history at Screening. For planned procedures/hospitalisations during the trial, documentation should be completed at the time of the Screening.

### **7.3.3 Ulcerative Colitis History and Previous Therapy for Ulcerative Colitis**

The date of diagnosis of UC, as well as previous and concomitant treatments for UC, will be recorded separately in the e-CRF during the Screening Visit.

### **7.3.4 Concomitant Medication Review**

Data concerning concomitant medications and procedures will be collected throughout the trial at all site visits. These data will be obtained at scheduled or unscheduled trial visits based on information provided spontaneously by the patient or as a result of questioning the patient.

### **7.3.5 Urine Screening for Drugs of Abuse**

At the Screening Visit, a urine drug screening (e.g. cocaine, barbiturates, amphetamines, opiates, benzodiazepine, and cannabinoids) will be performed. Clinical significance of a positive urine drug screen will be assessed by the Investigator.

## **7.4 Drug Concentration Measurements**

In PK subgroup, TJ301 levels will be monitored during the course of the trial. The clearance of TJ301 can potentially be affected not only by the presence of anti-TJ301 antibodies but also by disease activity including protein loss through severely inflamed colonic mucosa (21).

## **7.5 Handling of Biological Samples**

A central laboratory will be used in this trial for Anti-TJ301 antibodies, TJ 301 PK, IL-6, IL-6/sIL-6R complex, and faecal calprotectin tests. Sampling tubes, material for shipment of the samples, and a laboratory manual detailing all sample collection and shipment procedures will be provided and distributed to the trial sites by the central laboratory.

Except for PK subgroup patients, the total amount of blood planned to be collected from each patient who will be enrolled during the course of the trial is approximately 200 mL.

For PK subgroup, the total amount of blood planned to be collected from each patient during the course of the trial is approximately 300 mL.

## **8 ADVERSE EVENTS**

### **8.1 Adverse Event Definition**

An adverse event is any untoward medical occurrence in a patient participating in a clinical trial. It includes:

- Any unfavourable and unintended sign, symptom or disease temporally associated with the use of the IMP, whether or not considered to be caused by the IMP.
- Adverse events commonly observed and adverse events anticipated based on the pharmacological effect of the IMP.
- Any laboratory abnormality, vital sign or finding from physical examination assessed as clinically significant by the Investigator (pre-existing conditions diagnosed through assessments and examinations at the screening visit or during the screening period are not adverse events, but are recorded as medical history).
- Accidental injuries, reasons for any change in medication (drug and/or dose), reasons for any medical, nursing or pharmacy consultation, or reasons for admission to hospital or surgical procedures.
- Overdoses and medication errors with and without clinical consequences.

### **8.2 Collection and Recording of Adverse Events**

#### **8.2.1 Collection of Adverse Events**

The Investigator must monitor the condition of the patient throughout the trial from the time of obtaining informed consent until the last visit.

The sources of adverse events cover:

- The patient's response to questions about his/her health (a standard non-leading question such as "How have you been feeling since your last visit?" is asked at each visit).
- Symptoms spontaneously reported by the patient.
- Investigations and examinations where the findings are assessed by the Investigator to be clinically significant changes or abnormalities.
- Other information relating to the patient's health becoming known to the Investigator (e.g. hospitalisation).

#### **8.2.2 Recording of Adverse Events**

The Investigator must record all adverse events in the Adverse Event Log provided in each patient's e-CRF with information about:

- Adverse event
- Date of onset (time can be recorded, if applicable)
- Intensity

- Causal relationship to IMP
- Action taken to IMP
- Other action taken
- Date and time of outcome
- Outcome
- Seriousness

Each of the items in the Adverse Event Log is described in detail in the following sections.

### **Adverse Event**

Adverse events should be recorded as diagnoses, if available. If not, separate signs and symptoms should be recorded. One diagnosis/symptom should be entered per record.

If a patient suffers from the same adverse event more than once and the patient recovers in between the events, the adverse events should be recorded separately. If an adverse event changes in intensity, a worst-case approach should be used when recording the event, i.e. the highest intensity and the longest duration of the event.a

Note the following: A procedure is not an adverse event; the reason for conducting the procedure is. Hospitalisation is not an adverse event; the reason for hospitalisation is. Death is not an adverse event, but the cause of death is (an exception is sudden death of unknown cause, which is an adverse event).

### **Date and Time of Onset**

The date of onset is the date when the first sign(s) or symptom(s) were first noted. If the adverse event is an abnormal clinically significant laboratory test or outcome of an examination, the onset date is the date the sample was taken or the examination was performed.

For pre-existing clinically significant conditions (diagnosed or observed as a result of the screening procedures) becoming worse after IMP administration, the date of onset is the date the worsening began.

---

a Exception: an adverse event with onset after enrolment but before the first IMP administration (i.e. a pre-treatment adverse event), which changes in intensity after IMP administration, must be recorded as two separate events. The initial adverse event should be recorded with outcome “not recovered” and the date and time of outcome is when the intensity changed. The second adverse event should be recorded with date and time of onset when the intensity changed.

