### **9.8.2 Adverse Events**

A pre-treatment adverse event will be defined as an adverse event which occurs between signing the informed consent form and before the first dose of the IMP. A treatment-emergent adverse event (TEAE) will be an adverse event which occurs in the time interval from time of start of the first dose of the IMP up to 28 days after the Follow-up Visit. If an adverse event on Day 0 occurs before administration of IMP, it will be recorded as a pre-treatment adverse event. A post-treatment adverse event is any adverse event occurring after the patient's last visit (see also Section 8.6.2).

Treatment-emergent adverse events will be tabulated by SOC and PT using the currently available MedDRA version. The total number of patients reporting an adverse event, the percentage of patients (%) with an adverse event, and the number of events (E) reported will be presented.

Summary tables will be prepared for:

- All adverse events
- Adverse events by causality (reasonable possible/no reasonable possible)
- Adverse events leading to death
- Adverse events by intensity
- Adverse drug reactions by intensity
- SAEs
- Adverse events leading to withdrawal

A separate data listing will be provided of pre-treatment and post-treatment adverse events.

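### Footnote a in Section 8.2.2 re-records a pre-treatment event that improves after dosing as a new event, and Section 9.8.2 then counts it as treatment-emergent

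*Protocol*

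**What the plan says.** Section 8.2.2, under the heading Adverse Event, sets a general rule: when intensity changes, one record is kept on a worst-case basis, with "the highest intensity and the longest duration of the event". Footnote a makes an exception for an event that begins after enrolment and before the first dose, described there as a pre-treatment adverse event. Such an event, "which changes in intensity after IMP administration, must be recorded as two separate events". For the first record: "The initial adverse event should be recorded with outcome “not recovered” and the date and time of outcome is when the intensity changed". For the second: "The second adverse event should be recorded with date and time of onset when the intensity changed".

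Under Date and Time of Onset, the rule for clinically significant pre-existing conditions is narrower. It applies to those "becoming worse after IMP administration, the date of onset is the date the worsening began".

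Section 9.8.2 defines a treatment-emergent adverse event as "an adverse event which occurs in the time interval from time of start of the first dose of the IMP", with the window closing 28 days after the Follow-up Visit. It sets no condition that the event be new or worse. These events are tabulated by system organ class and preferred term, with patients, percentages "and the number of events (E) reported will be presented".

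**The concern.** Read together, the two rules turn some improvements into treatment-emergent events. The footnote creates a record with a post-dose onset, and Section 9.8.2 asks only when the onset was.

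Adverse events are a primary endpoint (Section 2.2), and the safety comparison consists of these counts, since no between-arm testing is planned (Section 9.8.1). With 30 patients per arm, one patient is 1/30 = 3.3 percentage points. A table that mixes improving events with new or worsening ones does not measure what its title says. The individual record also misdescribes the patient's course, because an event that is getting better is closed as not recovered and followed by an apparently new one.

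**Working it through.** **Text check**

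1. *Does the footnote cover improvement?* It uses the verb *changes*. The sentence it modifies uses the same verb and keeps the highest intensity whether that came first or last, so there the verb covers both directions. Where the protocol means deterioration it says so, as in the pre-existing-condition rule and in Sections 7.1.2 and 7.1.4. Nothing limits the footnote to increases.
2. *Can an event improve without ending?* Yes. The intensity scale has three grades, so severe to moderate and moderate to mild are both changes in intensity. Full recovery is an outcome and not a grade, so an event that simply resolves is not split.
3. *What onset does the second record get?* The time of the change, which is after dosing.
4. *Does that record meet Section 9.8.2?* Yes. It falls in the window "from time of start of the first dose of the IMP up to 28 days after the Follow-up Visit", and nothing else is required.
5. *Does the rest of Section 8.2.2 agree?* No. Date of Outcome lists recovery, death or worsening, but not improvement. The outcome list offers Recovering, yet the footnote imposes not recovered on an improving event.

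Example: a headache begins between consent and the first dose at moderate intensity and eases to mild on Day 3. The footnote yields one pre-treatment record closed on Day 3 and one mild headache with onset on Day 3, which is treatment-emergent.

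**Size**

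The protocol states no figure to reproduce and gives no rates. The only input from the document is 90/3 = 30 patients per arm. The following are assumptions:

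- q, the share with an unresolved pre-treatment event at first dose: 5%, 10% or 20%.
- p, the probability that it improves by a grade without resolving: 20% on placebo, 30% to 50% on active.

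Expected records created by improvement alone = 30 × q × p.

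| q | 30 × q | Placebo (p = 20%) | Active (p = 30% to 50%) |
|---|---|---|---|
| 5% | 1.5 | 0.3 | 0.45 to 0.75 |
| 10% | 3 | 0.6 | 0.9 to 1.5 |
| 20% | 6 | 1.2 | 1.8 to 3.0 |

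If the drug does not affect the event, p is 20% in every arm and the counts are equal.

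**Net direction**

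The footnote also splits events that worsen. Total splits = 30 × q × (p + w), where w is the assumed probability of worsening. At q = 10%:

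| Improve, placebo / active | Worsen, placebo / active | Total splits, placebo | Total splits, active |
|---|---|---|---|
| 20% / 40% | 20% / 10% | 3 × 0.40 = 1.2 | 3 × 0.50 = 1.5 |
| 20% / 30% | 20% / 10% | 3 × 0.40 = 1.2 | 3 × 0.40 = 1.2 |
| 20% / 30% | 30% / 10% | 3 × 0.50 = 1.5 | 3 × 0.40 = 1.2 |

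The total can be higher, equal or lower on active.

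**After the change**

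Only worsening is split. In the first row this gives 3 × 0.20 = 0.6 on placebo and 3 × 0.10 = 0.3 on active, and improvement contributes none.

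**The case against.** **The pool is narrow.** Sections 7.1.2 and 8.1 send conditions diagnosed through screening assessments to medical history, where the worsening rule applies. Enrolment in the footnote is not defined. If it means randomisation, that and the first dose both fall at Visit 2 and almost nothing qualifies. The first point stands and keeps the effect small. The second is weaker, because the footnote equates its scope with pre-treatment adverse events, which Section 9.8.2 starts at consent.

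**The rules cover different categories.** The worsening rule is for pre-existing conditions and the footnote is for events already recorded as adverse events. That is so, but it gives no reason to treat improvement as a new event in one category only.

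**The analysis can repair it.** Both records carry intensity and dates, and the statistical analysis plan, not shown here, could require new or worsened intensity. It could. But the recording rule is mandatory, the protocol states the definition itself, and the log items listed in Section 8.2.2 include no link between the two records.

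**Safety is descriptive.** This limits the consequence but does not make the counts correct.

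**A stronger reading that does not hold.** A reader might infer that an effective arm will collect more of these events and that the safety table is therefore biased against TJ301. The documents do not support this. It needs pre-treatment adverse events that the drug eases, whereas the symptoms of active ulcerative colitis at entry are the disease under study, and unrelated events give no reason for a difference. Events that resolve outright are not split, and fewer worsenings on active can offset or reverse the difference.

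**Conclusion.** The wording is wrong as it stands. The footnote in Section 8.2.2 and the definition in Section 9.8.2 together tabulate the improvement of a pre-treatment event as a treatment-emergent event, and no other passage prevents it. This conclusion rests on the text and needs no assumed rate.

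The size is probably small: about 0 to 3 patients per arm of 30 when 5% to 20% carry an unresolved pre-treatment event and 20% to 50% of those improve by a grade without resolving. All of these rates are assumptions. The effect on the percentage with any treatment-emergent event is smaller still, since a split adds a patient there only if that patient has no other such event. A difference between arms is possible if the drug eases such events, but the net direction for total treatment-emergent events is not established. The change is still worth making, because the counts belong to a primary endpoint and the correction costs very little.

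**What to change.** In footnote a of Section 8.2.2:

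- Replace *changes in intensity* with *increases in intensity*.
- In both places, replace *when the intensity changed* with *when the intensity increased*.
- State that a pre-treatment event that stays the same or improves after dosing remains a single pre-treatment record.

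This keeps the useful part of the exception: a post-dose worsening is still separated from the pre-treatment record and not absorbed by the worst-case rule.

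In Section 9.8.2, define a treatment-emergent event as one with onset, or a pre-treatment event that worsens, on or after the first dose.

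The cost is a few words in the footnote, one clause in Section 9.8.2 and an update to the e-CRF guide. No visit, assessment or sample size changes.

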## **Intensity**

The intensity of an adverse event must be classified using the following 3-point scale:

- Mild: Awareness of signs or symptoms, but no disruption of usual activity.  
Moderate: Event sufficient to affect usual activity (disturbing).  
Severe: Inability to work or perform usual activities (unacceptable).

## **Causal Relationship to IMP**

The possibility of whether the IMP caused the adverse event must be classified as one of the following:

### Reasonable possibility:

There is evidence or argument to suggest a causal relationship between the IMP and the adverse event. The adverse event may occur as part of the pharmacological action of the IMP or may be unpredictable in its occurrence.

Examples:

- adverse events that are uncommon but are known to be strongly associated with IMP exposure.
- adverse events that are not commonly associated with IMP exposure, but the event occurs in association with other factors strongly suggesting causation, such as a strong temporal association or the event recurs on rechallenge.

### No reasonable possibility:

There is no reasonable evidence or argument to suggest a causal relationship between the IMP and the adverse event.

Examples:

- known consequences of the underlying disease or condition under investigation.
- adverse events common in the trial population, which are also anticipated to occur with some frequency during the course of the trial, regardless of IMP exposure.

## **Action Taken to IMP**

The action taken to the IMP in response to an adverse event must be classified as one of the following:

- No change (medication schedule maintained or no action taken)
- Withdrawn
- Interrupted

